3.2.2 Contact

Selected women will be mailed a letter and information sheet introducing the study, followed by a telephone call by BMSR trained interviewers approximately one week after mailing the letter. The interviewers will attempt to contact their assigned list of potential participants by phone. They will make at least 10 attempts (calling at different times of the day, weekday, and weekends) to reach the listed county resident. After 10 attempts, if they have not been able to reach the participant, they will send a "no contact" letter to request that the participant contact the project office. Potentially eligible women may also contact us via a toll-free number or the study email address to participate. With prior approval from the potential participant, text messaging may be employed. Email may be used to communicate with and respond to potentially eligible women once they initiate communication with the project and permission is obtained to do so. The content of the emails or text messages will depend on the information requested by or needs of the participant. The project staff will not initiate communication by email or text without the permission of the potential participant.

Figure 3 summarizes communications between study staff, participants, and clinics.

Women who click targeted ads will be taken to a REDCap landing page (go.osu.edu/RISE) with a brief description of the study, eligibility criteria, and a brief set of questions to partially assess eligibility and determine best time for an interviewer to contact her to complete the consent process and baseline survey.

3.2.3 Consent for Participation

Once the participant is reached, the study will be explained, permission to verify eligibility will be obtained, the eligibility screener will be administered and if eligible, informed verbal consent will be obtained. After the verbal consent process is completed, the baseline telephone survey (1a) will be administered.

3.2.4 Eligibility Verification

After completion of the baseline telephone survey, participants will be mailed a medical record release form with a stamped, pre-addressed envelope to mail the medical record release form back to the OSU study office. Those who do not return the release form within two weeks will be re-contacted by the interviewer. Study staff will review and verify screening tests received by MRR and if the woman is still eligible, she will be enrolled and randomized to one of 3 study arms. The trained interviewers will be familiar with screening, determining eligibility, administering telephone surveys, and have a keen understanding of rural culture.

3.3 Randomization

Once eligibility is confirmed via medical record review, participants will be randomly assigned to one of 3 study arms -1)TIDVD alone, 2)TIDVD + PN, or 3)UC. A centralized web-based system at OSU will be used to randomize participants to one of the 3 study arms. Randomization will be stratified by age (50-64 vs. 65-74) and by seven screening categories representing which screening test(s) each woman needs (BC, CC, CRC, BC+CC, BC+CRC, BC+CC+CRC, or CC+CRC).

3.4 Data Collection and Measurements

Trained interviewers will collect data via REDCap (Research Electronic Data Capture) at baseline, 2 and 12 months from date of enrollment, and these data may also be collected using paper-based surveys (Teleform). We will collect information on outcomes as well as covariates and mediators. Self-report of cancer screening will be obtained at baseline, 2 and 12 months with MRR data collected at baseline and 12 months to verify screening status. Most recent height and weight measurements will be collected from chart review. Variables such as demographics that will not change will be measured only at baseline. The 12 month survey will also include open-ended questions to assess why women are adherent to specific cancer screening tests and not adherent to other screening tests. Constructs to be measured are described below and when each will be collected in Table 2.

3.4.1 Participant Surveys

Participants will complete surveys which will address demographics, medical history, health insurance, personal cancer screening history, cancer screening knowledge and beliefs, perceived cancer risk, benefits and barriers of cancer screening, self-efficacy, social support, and satisfaction with intervention materials. Surveys will be administered at baseline via telephone (1a) and paper (1b), two months into the intervention (TIDVD and TIDVD+PN arms) via phone (2) and at 12-months via paper (3).

Figure 4: Contact Flow Diagram

[figure not shown]

 Table 2. Data Collection: Constructs and Time Points

		Data	Collection	Collection Timing		
	Baseline 2		2-month	12-month		
	1a	1b	2	3		
Demographics	х					
General Health/Co-Morbidities	х					
Social Support		х		Х		
Personal Cancer History	х			Х		
Cancer Risk/Worry		х	х	х		
Cancer Knowledge/Attitudes/Beliefs		х	х	х		
Screening: Behavior/Barriers/Benefits/Self-Efficacy		х	х	х		
Staging		х	х	Х		
Screening Intention		х	х	Х		
Satisfaction with DVD			х			
Satisfaction with Navigator			х			
Contamination				Х		
Medical Record Review	х			х		
1a) Baseline Telephone 1b) Baseline Paper 2) 2-month Phone 3) 12-month Paper						

3.4.2 Community-Level Variables

Effect of community (neighborhood) factors, using geographic information system (GIS), on outcomes of

receipt of needed screening tests will be evaluated. Participant addresses will be geocoded and accessibility to health care will be determined by measuring the number of facilities within a given distance of each geocoded address. Geocoded addresses will be spatially joined to a U.S. Census Topologically Integrated Geographic Encoding and Referencing (TIGER) zipcode shapefile containing demographic data. An area deprivation index score will be created using the health care accessibility variable and 21 U.S. Census data variables, including social and economic conditions (e.g. education, employment/occupation, housing conditions, income/ poverty, racial composition, residential stability).¹²⁻¹⁵ **3.5 Incentives**

A total of \$25 in incentives will be distributed to participants as a sign of gratitude for taking the time to complete and return the surveys. Amounts and timing are detailed in Table 3.

Table 3. Gift Card Distribution

Time	Action	Amount
Pre-enrollment	Complete phone survey and send medical record release	\$5
Baseline	Complete and return paper survey	\$10
Month 12	Complete and return paper survey	\$10

3.6 Training of Interviewers

Interviewers will be trained, supervised, and monitored by the BMSR staff, in collaboration with the PIs and the Program Managers. Training manuals for interviewers developed for prior studies will be modified for the proposed study and will include: 1) overview of study objectives; 2) description of interventions; 3) protection of human subjects, HIPAA, and confidentiality issues; 4) cultural sensitivity; 5) roles and responsibilities; 6) documentation and reporting requirements; 7) data monitoring and quality assurance procedures; 8) handling problems/questions during recruitment/data collection; 9) effective interviewing techniques; and 10) use of the REDCap telephone interview system. Following practice sessions, interviewers will role-play and receive feedback until they have reached 100% compliance with recruitment and data collection integrity.

3.7 Quality Assurance

Performance of interviewers will be closely monitored by the project manager and the BMSR supervisors. Approximately 10% of all interviews and recruitment calls will be monitored for quality assurance purposes. Feedback will be provided to the interviewers to correct performance weaknesses.

3.8 Medical Record Review (MRR)

Participants will be asked to sign and return a MRR form to the study office after the baseline interview. The signed release will remain valid for the duration of the study. Dates and results of completed BC, CC, and CRC screening tests and confirmation of participant date of birth (DOB) will be requested from health care providers named by participants during the baseline and 12-month interviews. We are confirming DOB to ensure that records are obtained for the correct woman. The MRR form signed by the participant along with a request from our research office will be presented to the medical facility (secure fax, phone, secure email, or in-person) where the cancer screening tests were ordered or performed. This request will inform the clinic/facility staff about the study and request information from the medical record about the participant's cancer screening history to be sent to a secure fax or mailed to the study office at OSU. Women who report never being screened and/or cannot produce provider names or locations will be asked to complete MRR forms in order to contact locations that they may visit for screenings during the study period. Non-responders will be contacted again, if necessary, to obtain this information. We anticipate that at least 85% of the participants will return a signed MRR form, and 95% of clinics will respond to our request for information (based on our prior studies).¹⁶

[figure not shown]

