
4.3 Tailored DVD + PN

The second intervention group will receive a TIDVD intervention followed by a telephone call from a PN. **4.3.1 PN Intervention**

PNs will attempt to contact participants by telephone within 1 week after mailing the DVD. PNs will make at least 10 attempts at different times and on different days, including weekends, if needed. This timeframe will allow women to have received the DVD and watched it. If not viewed, the PN will encourage women to view the DVD and will assist to facilitate this. The PN will reinforce the DVD message and address barriers to receiving needed screening tests, including those not mentioned in the DVD. PNs will complete electronic encounter forms during each participant contact and have a file for each navigated participant. The encounter forms will include: 1) days/times of contact attempts; 2) a summary of the telephone call with documented cancer screening barriers; 3) navigator actions to address screening barriers; and 4) time spent on the call. PNs will track any other actions taken to assist participants (e.g. arrange transportation)

and track the time taken to complete those actions. PN information will be directly submitted to a database that will alert them when a follow-up action needs to be placed for a participant (e.g. an alert will be sent to the PN to call the participant to remind them of a cancer screening appointment). PNs will make as many contacts as needed to assist participants to complete screening tests.

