5.1.2 Primary Outcome

The primary outcome of adherence to screening guidelines at 12 months for Hypotheses 1 and 2 will combine MRR and self-report by using MRR when available and self-report otherwise. We anticipate obtaining MRR and verification on screening tests at the 12-month survey. Participants will be asked to provide contact information on both their primary care physician and any specialist who provided a screening test, reducing the chance of missing a test that was conducted but not reported to the primary care physician. For those who are lost to follow-up, a signed MRR form will enable us to obtain the adherence outcome for those participants. Thus, we anticipate adherence for the overwhelming majority of patients will be based on MRR. [name] will supervise these analyses with assistance from [name].

For hypotheses 1 and 2, the differences in binary adherence (Hypothesis 1, all needed screenings; Hypothesis 2, any needed screening) across the three randomized arms will be tested initially with pairwise chi-square tests. Binary logistic regression analysis will be used to compare the two interventions

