5.4 Quality Assurance for Intervention Fidelity

Evaluation of intervention processes is needed to ensure consistency of intervention delivery. Modifications will be made as necessary and recorded to ensure appropriate intervention delivery and maintenance of protocol integrity. Evaluation questions will assess user experience/satisfaction with the intervention. A random sample of participants per month will be called by the project manager to confirm receipt of the DVD and PN calls. The 2-month process evaluation survey will contain questions about the DVD or DVD+PN to serve as a rough manipulation check allowing us to document whether participants viewed the DVD or spoke to navigators. The BMSR will provide quality checks on 10% of the PN calls to document that the telephone

call was made, if cancer screening barriers were reported, and the actions discussed match the PN document.

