5.7 Management Plan

Overall study responsibility belongs to Drs. [name] and [name], Co-PIs of the study. [name] and her staff will be responsible for day-to-day study oversight including obtaining human subjects approval,

drawing/recruiting the sample, conducting interviews and the PN intervention, and data management activities. [name] and her staff will be responsible for the refining and troubleshooting the TIDVD and supervising the data analyses. [name] will assist in training the PNs and overseeing the process evaluation. [name] will assist with refinement of the DVD program and study measures. [name] will serve as the team clinician to advise about medical-related issues and to provide expertise related to clinical environments which serve these women. [name] will lead the cost analysis with assistance from [name], and [name] will lead data analysis with assistance from [name].

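### The 12-month record search and adherence coding are not masked to study arm or kept apart from navigator data, so the plan does not rule out better record finding in TIDVD+PN

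*Combined protocol and SAP*

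**What the plan says.** - **Outcome source.** Section 5.1.2 defines the primary outcome so that it "will combine MRR and self-report by using MRR when available and self-report otherwise".
- **Provider rule.** Under section 3.8, dates and results "will be requested from health care providers named by participants during the baseline and 12-month interviews". The research office sends the request, and replies come back to the OSU study office. Non-responders are re-contacted where needed, with no set number of attempts.
- **Safeguards in all arms.** Section 5.1.2 adds: "Participants will be asked to provide contact information on both their primary care physician and any specialist who provided a screening test". Section 3.8 keeps the release valid for the whole study and asks women who cannot name a provider to sign releases for places they may use.
- **Who reviews.** Section 3.2.4 says, for baseline eligibility, "Study staff will review and verify screening tests received by MRR". No section says who does this at 12 months, or that they are unaware of study arm.
- **Who does what.** Section 5.7 makes one lead and her staff responsible for "drawing/recruiting the sample, conducting interviews and the PN intervention, and data management activities". Section 5.4 adds: "The BMSR will provide quality checks on 10% of the PN calls".
- **Navigator files.** Section 4.3.1 says "PNs will complete electronic encounter forms during each participant contact and have a file for each navigated participant". Its database issues alerts; in the example given, "an alert will be sent to the PN to call the participant to remind them of a cancer screening appointment". This applies to TIDVD+PN only.
- **Other data that differ by arm.** The 2-month phone survey goes only to the two intervention arms (section 3.4.1).

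**The concern.** The participant and the navigator cannot be masked in this trial. The staff who request, abstract and code records can be. A completed test counts only if the right facility is asked and answers, so the outcome partly measures search effort. The plan leaves some of that effort to judgement, because the number of re-contacts is not fixed.

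Navigation is also meant to help women with no regular source of screening (section 4.3.3), so a provider list given at baseline may miss the site where a test was done. Section 5.1.2 relies on the signed release for women lost to follow-up. If such a woman gives no 12-month information, the plan's rule leaves only baseline providers and locations. In TIDVD+PN alone, a navigator file might show where to look.

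If that knowledge reached the search or the coding, the extra tests found would look like an effect of navigation in the comparisons named in Hypothesis 1. The plan already shows this kind of care elsewhere: the text under section 4.1 delays navigator contact about abnormal results until outcomes are collected, so that the results are not disturbed.

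**Working it through.** **1. Check of the method.** The plan gives no figure on this point, so I first confirmed that a pooled two-proportion z-test matches its calculations. The test level is not stated; 5% is assumed. For the secondary outcome in Table 5, at 376/376/200, it gives 80.0% (35% vs 45%, two-sided), 80.0% (25% vs 35%, one-sided) and 99.9% (25% vs 45%, one-sided). Table 5 states 80%, 80% and 99%. The primary-outcome row does not reproduce from its printed rates; that is a separate matter and does not affect this point.

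**2. How many completers could be missed.** The concrete route is women lost by 12 months. Planned attrition is 10% (section 5.1.1). Assume completion is no higher among them than among the rest. Then at most 10% of completers are in this group.
- A quarter of them missed: 0.25 × 10% = 2.5% of all completers.
- Half missed: 0.50 × 10% = 5%.
- All missed: 10%. A 15% miss cannot arise by this route.

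**3. Effect on the error rate.** Let T be the same true completion rate in both arms, and m the share missed in the comparator only (none missed in TIDVD+PN). Then:
- p1 = T(1 − m), p2 = T, d = p2 − p1
- p̄ = (n1p1 + n2p2)/(n1 + n2)
- s0 = √[p̄(1 − p̄)(1/n1 + 1/n2)]
- s1 = √[p1(1 − p1)/n1 + p2(1 − p2)/n2]
- Two-sided rejection = Φ((d − 1.96 s0)/s1) + Φ((−d − 1.96 s0)/s1)
- One-sided rejection = Φ((d − 1.645 s0)/s1)

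Example, TIDVD+PN vs TIDVD, T = 30%, m = 5%, 376 per arm: p1 = 0.285, d = 0.015, s0 = 0.03318, s1 = 0.03317. Rejection = Φ(−1.508) + Φ(−2.413) = 0.074.

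Example, TIDVD+PN (376) vs UC (200), same T and m: s0 = 0.03990, s1 = 0.03972. Rejection = Φ(−1.275) = 0.101.

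| True rate in both arms | Missed in comparator only | Observed difference | vs TIDVD, two-sided | vs UC, one-sided |
|---|---|---|---|---|
| 20% | 2.5% | 0.5 points | 5.3% | 6.6% |
| 20% | 5% | 1.0 point | 6.4% | 8.6% |
| 30% | 2.5% | 0.75 points | 5.6% | 7.2% |
| 30% | 5% | 1.5 points | 7.4% | 10.1% |

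The rates of 20% and 30% are the Table 5 primary-outcome figures for the two intervention arms. At the printed UC rate of 10%, the same formulas give 5.2% and 5.6% (vs TIDVD) and 6.0% and 7.2% (vs UC).

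**4. Extreme bounds.** With 10% and 15% missed, the two-sided error is 10.7% and 18.5% at a true 20%, and 14.9% and 28.0% at a true 30%.

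**5. Comparison with the planned effect.** At a true 30%, producing the whole planned 10-point difference would need a capture gap of 10/30, or about 33 percentage points.

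**6. Sample size used.** The figure of 376 is the number after 10% loss. If lost women were recovered through records, up to 418 per arm would be analysed. For T = 30% and m = 5%, s0 is then about 0.0315 and the two-sided error 7.6% instead of 7.4%.

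**The case against.** The strongest reply is that the plan already sets one search rule for all arms: providers come from the participant, and both primary care and specialist contacts are requested. If the rule is followed, a facility known only to a navigator is not queried, so bias needs a departure from the plan. Navigators work full time on navigation (section 5.2.1), which points away from their handling records. The 12-month survey is on paper (section 3.4.1, although section 3.8 speaks of a 12-month interview), which limits interviewer influence. A different lead supervises the data analyses (section 5.7).

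Most of this stands, and it rules out several stronger readings that a reader might infer:
- *That the plan builds in a biased search.* It does not. It neither uses navigator files for the search nor forbids it.
- *That navigators or call auditors abstract records.* The overlap in section 5.7 is one of staff group and responsibility. No section gives an individual navigator this task, and nothing links the call audit in section 5.4 to the record search.
- *That navigator files list the facility and test date.* This is only implied by the example of a reminder alert. The listed encounter-form items are contact attempts, a call summary with barriers, actions and time.
- *That an error rate of 11% to 28% is to be expected.* Those figures need every missed test to be recovered in one arm and none in the other, and the 15% case exceeds what 10% attrition allows.

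What the reply does not answer is the silence on masking. A common provider rule does not fix the number of re-contacts, and it does not govern how an unclear record is coded by someone who knows the arm.

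**Conclusion.** The concern holds as a gap in protection. The plan does not prevent differential record finding or coding between arms; it does not cause it. The likely harm is a modest rise in false-positive error and some exaggeration of the navigation effect. It could not plausibly create the whole planned difference.

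The size is unknown. With 2.5% to 5% of true completers missed in the comparator only, the nominal 5% error becomes about 5% to 7% against TIDVD and about 7% to 10% against UC. This rests on four assumptions: a 5% test level, equal true rates of 20% to 30%, no misses in TIDVD+PN, and completion among lost women no higher than among the rest. The plan gives no record-capture figure by arm that would narrow the range. Severity is minor to moderate. It is worth correcting because masking this step is feasible and cheap.

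**What to change.** In sections 3.8 and 5.7, state that:
1. Staff who send 12-month record requests, abstract the records and code adherence work from a list without study arm, and have no access to the navigator encounter database or the 2-month process data.
2. The participant-named provider rule applies in every arm with the same fixed number of re-contacts. Navigator files are not used to choose facilities or to score a test.
3. Record availability and the use of self-report are reported by arm, so that readers can judge whether capture differed.

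The cost is protocol wording, restricted database permissions and some reallocation of tasks among existing staff. A few true tests known only from navigator files will not count, which slightly lowers the observed TIDVD+PN rate. The sample, the interventions and the endpoint do not change.

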4.0 Interventions

4.1 Conceptual Model for the Intervention

A multiple health behavior change intervention is especially appealing when addressing behaviors that are conceptually similar, such as cancer screening behaviors. Cancer screening behaviors have many commonalities and have been found to be correlated with common variables predicting screening for all 3 tests.¹⁷ For example, the theoretical principles used to make behavior change for each cancer screening test include self-efficacy, and the use of change processes that move an individual through stages of change.¹⁸⁻²⁰ The interventions proposed will focus on the needed cancer screening tests concurrently

and teach principles of behavioral change (e.g. self-efficacy). Several studies have found that interventions targeting multiple behavior change (but none have focused on 3 screening test behaviors) have been effective in simultaneously changing up to five behaviors. In 2005, a randomized controlled trial was effective in helping CRC patients change multiple behaviors.²¹ More recently, researchers found that an intervention targeting multiple behaviors was successful in decreasing sedentary behavior in CRC survivors.²² Johnson coined the word coaction to reflect the synergistic effect one behavior can have on another.²³ He concluded that regardless of study design or other variability, coaction was consistently found in multiple behavior studies.

The conceptual model (Figure 5) uses constructs from the Theory of Reasoned Action, Theory of Planned Behavior, as well as other well-established behavioral theories.²⁴⁻²⁷ This model will build on previous work by identifying an individual's beliefs about variables known to predict behavior change.^{24,28,29} These variables will have intervention messages tailored to each women's input. Our goal is to provide a unified intervention that supports adherence to all 3 cancer screening tests, depending on individual screening needs. Responses are tailored to specific tests needed by the individual. Ability to carry out tests will vary based on which test is being discussed and the program will tailor messages appropriate to the test(s) needed.²⁸⁻³⁰ Variables that may affect beliefs directly or indirectly such as demographics, health care provider input, and social conditions and policies are identified in Figure 4. This model will be used to identify intervention effects and to test model development. Intervention "engagement" has been identified by researchers and theorists as a critical component of intervention effectiveness and will be measured and included in the analyses.³¹

